12.10 METHODS TO HANDLE MISSING DATA

For missing outcome data, the results from the linear mixed models are valid under a missing at random (MAR) missing data generating mechanism that allows for fixed effects and earlier outcome values to predict missingness of later ones.

Considering incomplete baseline measures: although baseline data should be complete prior to randomisation, there may be some limited missing data. Descriptive baseline summaries will be presented as complete case. The proportion of missing data will be summarised by scale/assessment. If any of the baseline measures are found to relate to missing primary outcome at 6 months we will consider adjusting for them in models for the primary outcome. To allow for this, any baseline measure considered as a covariate in the main model would best be imputed to a full single dataset. Missing baseline covariate data will therefore be imputed using the missing indicator method where a dummy variable for missingness will be included as a covariate in the model for binary data, and mean imputation for continuous data, as per the recommendations of White and Thompson (2005).

12.11 PLANS TO GIVE ACCESS TO THE FULL PROTOCOL AND PARTICIPANT LEVEL-DATA

It is anticipated that the full protocol and all results will be available as open access according to the rules of the funding body, the National Institute of Health Research (NIHR).

13 MEASUREMENT OF COSTS AND OUTCOMES

13.1 WITHIN-TRIAL HEALTH ECONOMIC EVALUATION

This will:

- a. Estimate resource use and costs in each arm over 1 year in adults with moderate to severe eczema.
- b. Estimate QALYs in each arm over 1 year in adults with moderate to severe eczema.
- c. Undertake a within-trial cost-utility analysis to assess the value for money of different treatment options for moderate to severe atopic eczema in adults for NHS provision.
- d. Estimate uncertainty levels associated with the decision about treatment provision.

13.1.1 ECONOMIC DATA COLLECTION

Resource use associated with the treatment options (drug use, monitoring and adverse events) will be recorded during the 12-month treatment period. Wider resource use (primary care visits, prescriptions, other health contacts) will be regularly collected via the patient facing electronic tool (baseline and months 3, 6, 9 and 12) and participants will be offered study diaries to act as an aide memoire.

13.1.2 ECONOMIC EVALUATION ANALYSIS

Costs will be estimated from the perspective of the NHS and Personal Social Services³⁸, by attaching published unit costs for the most recent price year (example sources include Jones et al 2024, NHS England 2021/22, NHSBSA 2022/23)³⁹⁻⁴¹. Wider resource impacts on the participants, in terms of employment and out of pocket costs, will be analysed separately. The utility score from the EQ-5D-5L will be used to estimate QALYs for the trial period using linear interpolation and area-under-the-curve analysis with and without adjusting for baseline differences⁴². We will value the EQ-5D-5L in our primary analysis in line with NICE recommendations at the time of analysis.

The economic evaluation will estimate the mean incremental cost and mean incremental QALYs of the comparator drugs at 6 and 12 months (given the timeframe costs and benefits will not be discounted). A regression-based approach (for instance seemingly unrelated regression equations if assumptions are met⁴³) will be used to estimate the mean incremental cost and effects with and without adjusting for difference in baseline characteristics (EASI score, costs, EQ-5D, duration of disease) and minimisation factors (recruitment centre, severity). In line with the guide to handling missing data in within trial cost-effectiveness analysis⁴⁴, the pattern and nature of the missingness will be explored using descriptive analyses (e.g. amount of missing data by trial group at each time point; missing patterns; association between missingness and baseline variables; and association between missingness and observed outcomes). We will use this analysis to choose an appropriate method to handle any missing data.

Since cost data are likely to be skewed, we will use non-parametric bootstrapping to estimate mean (95% CI) incremental cost and mean (95% CI) incremental QALY. Treatment options will be ranked from least to most costly, any option that is strongly dominated (i.e. options which are inferior in terms of both cost and outcome) will be ruled out before estimating incremental cost effectiveness ratios (ICERs) and/or net monetary benefits as appropriate (NMBs). These will then be examined for extended dominance, where treatment options with a higher ICER than options that follow, will be removed and ICERs/NMB re-estimated. Bootstrapping will also be used to explore the level of uncertainty associated with the decision to adopt a treatment through the estimation of cost-

effectiveness acceptability curves (CEAC)⁴⁵. A range of ceiling ratio (or willingness-to-pay per QALY) values will be tested, including the £20,000 and £30,000 per QALY indicative thresholds used by NICE³⁸. We will conduct sensitivity analysis in relation to key assumptions, including alternative assumptions in relation to missing data. A health economics analysis plan (HEAP) will be finalised before the trial database is locked.

13.2 LONG-TERM HEALTH-ECONOMIC ANALYSIS

A disease-based decision-analytic model will be developed to evaluate the expected long-term costs and health consequences of moderate to severe eczema in adults. This will incorporate periods of disease relapse and remission, adverse events related to treatment and drug specific prescribing guidelines (e.g. ciclosporin use not recommended for >1 year). Sensitivity analysis will be used to explore assumptions made (i.e. about treatment duration, costs, disease severity and relapse rates post-treatment). The model form is likely to be a Markov-type model, where groups of patients move between defined health states (e.g. healthy skin, mild eczema, moderate eczema, severe eczema, death) using estimated probabilities of disease progressions for fixed time intervals. Model design will be finalised after: a) an updated review of existing eczema economic models⁴⁶; b) multidisciplinary input on model structure and data sources; and c) review of evidence for source data for model parameters. This process will be documented to interrogate the proposed model and reach agreement amongst those involved. Identification, selection and synthesis of relevant evidence sources will follow recommended methods and will use the primary data collected within BEACON and expert clinical input amongst the team. The Markov model will be developed in an open-source framework (excel/visual basic/R) to enable sharing. To demonstrate model credibility we will ensure transparency, face validity, internal validity (including sensitivity analysis using a broad range of values for all parameters to ensure the model behaves as expected according to the theoretical model) and model corroboration (a discussion of similarities and differences between the model produced and those already in the literature). An economic evaluation will be performed for an appropriately long-time horizon in line with the within trial analyses except all costs and benefits will be discounted at recommended rates to reflect the longer timeframe.

14 NESTED PROCESS EVALUATION

The process evaluation will consist of two distinct elements: (i) semi-structured 1:1 interviews with a sample of trial participants; and, (ii) an online survey of all those screened for inclusion.

14.1 INTERVIEW STUDY

14.1.1 PURPOSE

This nested study will seek insight from participants about the ongoing practical delivery of this platform trial as well as future implementation of systemic, immunomodulatory treatment in moderate to severe eczema. Specifically, it will investigate participants' expectations (including perceived benefits and risks of 'standard' vs targeted treatments) and experience of trial procedures (recruitment, data collection (including via the online platform), clinical tests including biological sample collection and ongoing involvement) and of treatment (benefits, side-effects, medication transitions).

This insight will support the maintenance of the trial, offering contextualised information about how best to approach, recruit and retain participants. It will provide important insight about how to support treatment changes at month 6. It will offer insight that will support the extension of this platform as

additional drugs and/or treatments for moderate to severe eczema are subsequently identified for inclusion.

Appreciating participant's expectations and experiences of systemic treatment will support the design and implementation of novel treatment pathways for moderate to severe eczema.

14.1.2 SAMPLE AND SELECTION

In the first instance a purposive sample of approximately 30 trial participants will be recruited to take part in this element of the research. As the trial proceeds, with each additional arm, 10 to 15 extra participants may be recruited. Participants will be selected to ensure that individuals from each arm of the trial are included. We will use baseline demographic and clinical data to ensure a diverse study population including 'hard to reach' populations (male/female, younger/older, ethnicity). Selecting participants in this way will ensure that findings are reflective of, and responsive to, a broad range of perspectives and experiences.

In addition, we will responsively recruit participants should any emergent issues arise in the delivery of the trial – such as difficulties with specific treatments or with particular research processes. In these cases, we will seek to interview those who withdraw from the trial or those who experience difficulties with treatment/research processes.

Participants who are selected for and willing to take part in the interview study following review of the PIL will be asked to complete and return the paper consent form prior to the first interview.

14.1.3 DATA COLLECTION AND MANAGEMENT

Most participants will be interviewed at two time-points – as soon as possible after of randomisation (ideally within 8 weeks), and then at the completion of the study, in order to gain insights into expectations prior to or at the start of treatment and experience following trial treatment completion. Some of these may be asked to take part in an additional interview should they change medication at month 6. Those participants recruited to explore an emergent issue may only be interviewed once.

All interviews will be semi-structured and 1:1 with open questions (see Interview Topic Guide provided separately) used to guide a discussion of experiences and opinions. Interviews will be flexible to allow participants the opportunity to introduce new topics and to focus in areas which they think are important. All interview data will be audio-recorded, transcribed in full and handled using the NVivo 12 software package.

Please see Appendix 8 for pre-consent data flow for the nested interview study.

Initial interview:

Initial interviews will explore patients' experience of eczema, their expectations of treatment (specifically considering whether the different treatments offered are typified by different expectations); and thoughts about participating in this trial, particularly around treatment allocation.

Interviews will explicitly explore knowledge of treatment options, feelings about their allocated treatment and their expectations for clinical outcomes and safety. Initial experience of treatment will also be discussed.

Later interview (on completion of participation):

Later interviews will reflect upon participants' experience of the trial, their experience of treatment(s) such as the benefits or difficulties of self-injection compared to oral treatment, adherence, or their experience of multiple treatments and the process of switching treatments.

Recommendations for future treatment use in the implementation of the findings of the study will be sought. Data generated (insight offered) in the early interviews will be revisited at later interviews to consider how participant expectations had been fulfilled or changed. Insight generated in this way will illuminate perceptions about systemic treatments for eczema, will help to identify common misapprehensions, and will support better clinical / research communication about systemic treatments in eczema management.

Ad hoc interviews (emergent issues):

Interview topic guides will be developed to explore ad hoc issues which emerge in the process of the trial. This might include a concern for participant withdrawal, for side-effects and medication difficulties, or for some other reason.

Patient contact details forms (referral forms for interview study received from hospital sites) and interview study consent forms will be kept alphabetically within a locked filing cupboard during the project. Within the electronic data, patients will only be referred to using study ID and so effectively interview recordings will be pseudonymised. Patient name and study ID are only linked on the referral forms that are received from the hospital sites (following consent to be contacted regarding the qualitative interviews) and the interview study consent forms.

We will use University of Nottingham (UoN) provided storage for our working data. UoN licenses Microsoft Teams, allowing for secure and controlled sharing of data among the research team only. Microsoft Teams encrypts data both in transit and at rest and is approved against the University's Handling Restricted Data Policy. The service provides several layers of automatic back up and, in a disaster scenario, files can be recovered. Access to data stored in MS Teams is via secure log-in with multi-factor authentication. There is a Teams channel for the BEACON study at the University of Nottingham with restricted access for only BEACON study team members.

Audio files will be stored with the following filename format: BEACONAUDIO_PID (PID=participant identification number) within the "Interview recordings" folder on the BEACON Microsoft Team. Transcription files will be stored with the following filename format:BEACONTranscript_PID in the "Transcripts" folder on the BEACON Microsoft Team. NVivo analysis files will the stored as "BEACON qualitative interviews" in the "Analysis" folder on the BEACON Microsoft Team.

14.1.4 DATA ANALYSIS

We will build upon previous qualitative eczema research by providing a detailed, contextualised assessment of individuals' experience of systemic treatment for moderate/severe disease.

An external audio transcription company will be assigned to transcribe and anonymise the interview recordings (other than study ID, no other identifiable information about participants will be shared with the transcription company). Data will not be transferred to the third-party transcription vendor until a service level agreement is in place to ensure confidentiality of the data. Interview transcripts will be reviewed and coded thematically using the NVivo 12 software package – identifying key insight, experiences or opinions. Coded interviews will be reviewed and compared to characterise recurrent and/or prioritised ideas about disease, treatment and the platform trial. Interview transcripts will be stored within a separate study file.

The perspectives of different participants will be compared and synthesised in this process in order to reflect upon similar and different experiences associated with the different treatments included in this trial. Participant assessment of their experiences (and treatment benefits / difficulties) will support conclusions about which treatments are most accepted and best tolerated.

Analytic codes and themes will be tested and refined as new data is considered. This process will cease when these codes/themes are considered stable and no longer growing or evolving.

14.2 BEACON PARTICIPANT ONLINE SURVEY

14.2.1 PURPOSE

Developed in collaboration with our PPI partners to gain a broad insight about participants' expectations of the medications included in this study, and to explore issues of medication adherence and acceptability.

14.2.2 SAMPLE AND SELECTION

All individuals who consent to screening and are eligible to take part will be provided with a link to a BEACON participant online survey (start of study) to complete via DrDoctor prior to randomisation at the baseline visit. At the 52 week clinical and safety assessment all participants will be provided with a link to a second BEACON participant online survey (end of study).

Any participant that leaves the study prior to the 52 week assessment will also be provided with a link to the second online survey.

14.2.3 DATA COLLECTION

Each online survey will include a small number of questions which broadly consider the acceptability of the medications being investigated here.

In the first survey potential participants will be asked about their knowledge of the medications, their expectations of benefits associated with them, perceived challenges associated with them, and any preference that they may have.

In the final survey they will be asked about their experience of taking the medications, to identify any difficulties associated with the medication, to indicate any strategies that they developed to support medication adherence, and any retrospective preference for specific medications.

14.2.4 DATA ANALYSIS

Data will be uploaded from DrDoctor to the NVivo 12 Software package and analysed alongside the qualitative interview data. To reflect that data will be generated digitally (online) and might vary in quality (some offering more detail than others) an iterative approach to analysis will be adopted. Keyword and keywords in context will offer a broad, summative form of content analysis; a more conventional thematic analysis will complement this with greater depth of insight where responses allow.

Analysis will consider each medication separately and will bring together insight from the screening and later online surveys. For each it will summarise participants' knowledge and expectations of the medication and will review issues of adherence and acceptability. For each medication a unique 'model' will be constructed.

Comparison of these models will allow comment on participants views of the different medications, and assessment about which is broadly considered more appropriate and acceptable.

15 LONG TERM FOLLOW UP

All trial participants will be invited to enrol into the UK-Irish Atopic Eczema Systemic Therapy Register (A-STAR). Participation in A-STAR will be optional. A-STAR is an observational study running in the UK and Ireland, collecting data on the short and long-term safety and effectiveness of systemic treatments for people with eczema (https://astar-register.org/) funded by the British Skin Foundation and the British Association of Dermatologists. Patients will be offered the chance to consent to A-STAR once enrolled in the Beacon trial. Data would subsequently be collected for BEACON and A-STAR, with no additional data collection needed for A-STAR over and above that required for BEACON in the first 12 months. This will contribute to this large-scale effort to establish the long-term safety and clinical outcomes of systemic treatments.

16 Allied Mechanistic Research

Our allied mechanistic research study, mySkinomics, will characterise the events underpinning eczema drug actions and outcomes to treatment, with a view to informing the design of novel therapeutics and personalised medicine approaches to management. The governance framework for this observational research is separate to BEACON, with independent consent. BEACON participants on methotrexate or dupilumab at participating sites will be invited to participate (their participation is optional).

17 CONTINUATION AS A MULTI-ARM MULTI-STAGE PLATFORM

This trial has adopted an adaptive multi-arm multi-stage platform trial design to facilitate the incorporation of new treatments and arms in the future as they emerge (see section 1.3 for information).

17.1 STATISTICAL CONSIDERATIONS

Each additional arm will be considered as a new parallel-group comparison against the nominated standard of care (currently ciclosporin). The advantages of considering these new comparisons in a future platform are multiple:

- a. statistical efficiency from the use of a single control group
- b. operational efficiency from adding a new arm into an existing protocol and database
- c. cost efficiency compared to setting up an independent parallel-group trial

Design considerations for MAMS trials include controlling the type 1 error rate. If the additional trial arms are different, the emphasis should be on controlling the pairwise error rate and powering each research arm separately, as though an independent trial⁴⁷. Therefore, there are no additional considerations for the three-arm trial at this stage, which already has a conservative pairwise adjustment of 0.025. If new arms are added late during the course of this study, there will be little overlap in shared control arm information, which will further reduce the correlation between the pairwise comparisons, and the need to change the type I error for the current arms. However, the timing of new arms will impact on the length of the study required to randomise a concurrent control group with the same eligibility criteria, and we may adjust the randomisation ratio to produce results from each comparison at a similar time.

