2 TRIAL DESIGN

This is a UK, multicentre, one year, assessor-blind, randomised controlled trial assessing systemic treatments in adults with moderate to severe eczema. Three mechanistic classes of drugs are being tested against a control (ciclosporin). Further treatments and arms may be added in future amendments.

Participants will be randomised in a 1:1:1:1 ratio. **During the first stage of the trial (months 1-6)**, **follow up will be face to face at 1, 3 and 6 months** for safety and effectiveness assessment (see Figure 2 for trial flow diagram and Table 1 for schedule of events). There are additional drug-specific safety only visits for some arms as shown in Table 1, Figure 2, and individual flow diagrams in drug specific Appendices 1-4, in line with routine care and national guidance. There is the **option to increase the treatment dose at 3 months for some arms if there has been an inadequate response** following which additional safety only visits may be required (see Table 1 schedule of events, Figure 2 trial flow diagram, and individual flow diagrams in drug specific appendices 1-4). Dose reduction will be permitted at any stage as clinically indicated and according to standard clinical practice. Safety only visits (when no additional effectiveness measure is conducted) can be conducted in the community where deemed appropriate by the investigator (general practice). If participants attend study sites, contact with study staff should be minimised and staff will be trained to not provide additional support to minimise performance bias.

The primary outcome will be assessed at 6 months. Responders, defined as those achieving at least a 50% improvement in the objective EASI score (EASI50) and $a \ge 4$ point reduction in Dermatology Life Quality Index (DLQI) will continue the same therapy for a further 6 months (up to 1 year) if they are tolerating the treatment and are happy to continue (in line with NICE guidance (NICE TA534¹⁷)). Non-responders will switch therapy in a pre-determined way that mirrors real world practice (see Figure 2).

In the second stage of the trial (months 7-12) face to face safety and effectiveness assessments will be at 9 and 12 months. For those participants who have switched therapy there will be an additional telephone/ remote safety only visit (with bloods) at 7 months. Dependent upon

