8 ASSIGNMENT OF INTERVENTIONS

8.1 RANDOMISATION METHOD

Randomisation is by the method of minimisation, balanced by recruiting study site and disease severity (moderate/ severe) and with a random component.

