12.2 STATISTICAL ANALYSIS PLAN

A full Statistical Analysis Plan (SAP) will be drafted in accordance with the KCTU Standard Operating Procedures authored and approved by the Trial Steering Committee and Data Monitoring and Ethics Committee.

The Junior Trial Statistician will be fully blind until the first version of the SAP is approved by the Data Monitoring Committee (DMC).

After the first version of the SAP is approved by the DMC, the Junior Trial Statistician will become unblinded and access participant level data by arm. The Junior Statistician will then have access to the adherence data and be able to monitor and inform the DMC of the trial adherence of the participants. They will present the closed DMC report to the DMC members.

The Junior Trial Statistician will not take part in any discussion that influences the early stopping of the trial at any TMG, TSC, or DMC meetings.

12.3 **GENERAL PRINCIPLES**

We will report data in line with the Consolidated Standards of Reporting Trials (CONSORT) for multiarm trials showing attrition rates and loss to follow-up. This will include the number of eligible patients, number of patients agreeing to enter the trial, number of patients refusing, then by intervention arm: the number of patients compliant/non-compliant with treatment, the number continuing through the trial, the number withdrawing, the number lost to follow-up and the numbers excluded/analysed at each time point.

Analyses will be carried out using the intention to treat principle: participants will be analysed in the group they are randomised to, and available data from all participants are included, including those who do not complete therapy. Every effort will be made to follow up all participants in all arms for research assessments. For estimates of treatment effects in each comparison, only participants who could have been randomised to either arm (i.e. not contraindicated to either drug and contemporaneously randomised) will be included in that comparison.

Analysis will be conducted in Stata version 17.0 or later.

12.4 **BASELINE CHARACTERISTICS**

No statistical significance tests or confidence intervals will be calculated for the difference between randomised groups on any participant level baseline variables. The randomisation of participants to intervention groups means that any imbalance over all measured and unmeasured baseline characteristics is by definition due to chance.

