12.5 STATISTICAL METHODS FOR PRIMARY AND SECONDARY OUTCOMES

12.5.1 STATISTICAL METHODS FOR PRIMARY OUTCOME

For the repeated measures of the continuous EASI score, linear mixed models will be fitted to the outcome variable at all time points. We will use a linear mixed model, with fixed effects of trial arm, time and a time*arm interaction term, baseline values of the EASI score and minimisation factors (recruitment centre, severity). Random intercepts will be fitted at the participant level.

Marginal treatment effects will be estimated for the EASI score at 6 months and reported as adjusted mean difference in scores between the comparative groups, its standard error, 97.5% confidence intervals and p-value. Significance level (type 1 error) will be two-sided at 0.025.

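### If the randomisation ratio within a comparator–ciclosporin pair is changed while both arms are open, the stated primary model has no recruitment-period term to prevent residual calendar drift from biasing that pair

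*Protocol*

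**What the plan says.** The allocation in force is equal. Section 2 states "Participants will be randomised in a 1:1:1:1 ratio", and the synopsis and sections 7.1 and 8.3.3 agree. Section 17.1, discussing the timing of new arms, adds that "we may adjust the randomisation ratio to produce results from each comparison at a similar time". It names no trigger, no new ratio and no consequence for the analysis.

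Section 12.5.1 sets out the primary analysis as a linear mixed model "with fixed effects of trial arm, time and a time*arm interaction term, baseline values of the EASI score and minimisation factors", the factors being centre and severity. On random effects it says "Random intercepts will be fitted at the participant level". The word time there means follow-up visit, since "linear mixed models will be fitted to the outcome variable at all time points". Section 12.5.2 carries the same approach to the continuous secondary outcomes.

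Two other provisions bear on calendar time. Section 12.3 limits each comparison to participants who were "not contraindicated to either drug and contemporaneously randomised". Section 8.1 describes minimisation as "balanced by recruiting study site and disease severity (moderate/ severe) and with a random component", so recruitment period is not a balancing factor.

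**The concern.** The concurrency rule in section 12.3 removes controls recruited before a comparator opened. It does not deal with a ratio change inside the window in which both arms are open. Participants from before and after the change are all concurrent, so they are pooled. If ciclosporin is up-weighted in the second part of that window, a larger share of the ciclosporin arm than of the comparator arm comes from the later period, and arm and period are then associated.

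If 6-month EASI also drifts between the periods, for reasons not captured by baseline EASI, severity or centre, the model attributes part of the drift to treatment. At stake are the primary estimate for that pair and its 2.5% error rate. Section 17.1 rests its multiplicity argument on that pairwise rate.

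**Working it through.** **Inputs from the protocol (sections 12.1 and 12.5.1).** Difference 6.6, SD 13.6, two-sided alpha 0.025 per comparison, 90% power, 20% loss, 134 randomised per arm.

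**Assumptions, not in the protocol.** Control:comparator goes from 1:1 to 2:1 (or 3:1) when half of the pair has been recruited. Residual drift D is 2 to 4 points in 6-month EASI between the two periods, after baseline EASI, severity and centre. There is no true treatment effect.

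**The plan's own figure.** n = 2 × 13.6² × (2.241 + 1.282)² / 6.6² = 105.4, so 106 evaluable per arm by the normal formula and 107 with the t distribution. 107 / 0.8 = 133.75, so 134. The stated number reproduces.

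**Share of each arm recruited after the change.** Take 214 evaluable in the pair, 107 in each period. Period 1 contributes 53.5 to each arm.
- 2:1 in period 2 adds 71.3 controls and 35.7 comparators. Totals are 124.8 and 89.2, late shares 57.1% and 40.0%, gap 0.171.
- 3:1 in period 2 adds 80.25 and 26.75. Totals are 133.75 and 80.25, late shares 60.0% and 33.3%, gap 0.267.

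**Bias and type I error.** |Bias| = D × gap. SE = 13.6 × √(1/n₁ + 1/n₂), which is 1.89 for 2:1 and 1.92 for 3:1. Type I error = Φ(−2.241 − bias/SE) + 1 − Φ(2.241 − bias/SE).

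| Change | Drift | Bias | Type I error |
|---|---|---|---|
| 1:1 to 2:1 | 2 | 0.34 | 2.7% |
| 1:1 to 2:1 | 4 | 0.69 | 3.5% |
| 1:1 to 3:1 | 2 | 0.53 | 3.1% |
| 1:1 to 3:1 | 4 | 1.07 | 4.8% |

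With the equal-arms SE of 13.6 × √(2/107) = 1.86, the last entry is 5.0% and the others are unchanged to one decimal. The sign depends on which arm is up-weighted and which way EASI drifts.

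**Simulation check.** 4,000 runs per scenario of a 6-month ANCOVA on baseline, with whole-number counts of 54:54 then 71 controls to 36 comparators (control:comparator 2:1):
- Residual drift 3, no period term: bias −0.46, type I error 3.0%. With a period term: 0.00 and 2.6%.
- Residual drift 6.6, no period term: bias −1.07, type I error 5.0%. With a period term: 0.05 and 2.7%.
- A 5-point drift carried wholly by baseline EASI, no period term: bias −0.01, type I error 2.6%.
- Ratio held at 1:1, residual drift 6.6, no period term: bias 0.02.
- Control:comparator held at 2:1 in both periods, residual drift 6.6, no period term: bias −0.04.

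This is a single-visit analysis. It confirms the mechanism but does not test the full repeated-measures model.

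**Price of adjusting (1:1 to 2:1).** The period-adjusted SE is 13.6 / √(53.5 × 53.5/107 + 71.3 × 35.7/107) = 13.6 / √50.5 = 1.91. Power at 6.6 is Φ(6.6/SE − 2.241): 89.6% without the term and 88.7% with it.

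**The case against.** The strongest reply is that nothing is wrong with the analysis of the trial as it now runs. The ratio clause is permissive and unused, and every operative section says 1:1:1:1. A new ratio would contradict those sections and so need an amendment, where the analysis consequence could be settled. Added covariates are also ordinary SAP content, and section 12.10 already contemplates further baseline covariates in the primary model.

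The aim of section 17.1 can moreover be met without harm. If a new arm enters at 1:1:1:2 and that ratio is held, the existing pairs stay 1:1. The new pair is 1:2 throughout its concurrent window, so no within-pair ratio changes. The same sentence of section 17.1 also calls for concurrent controls under the same eligibility criteria, which limits one source of drift.

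Most of this stands, and it confines the point to a conditional one. A reader might infer that the primary analysis is already biased, that adding abrocitinib biased the earlier comparisons, or that any time trend would do so. The documents do not support these readings. Pairs now run at 1:1, and they did so before abrocitinib if the three-arm stage also allocated equally, which this version does not restate. Trends carried by baseline EASI, severity or centre are already in the model.

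What survives is that the protocol both reserves the ratio change and lists its model terms. Using the two together as written would leave an affected pair unprotected.

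**Conclusion.** The point holds as a minor, conditional gap. It needs two things together: a ratio change within a pair while both arms are open, and a calendar trend in 6-month EASI beyond what baseline EASI, severity and centre explain. Neither is shown to have occurred.

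Under the assumed 1:1 to 2:1 change at mid-recruitment with 2 to 4 points of residual drift, the bias is 5% to 10% of the 6.6-point target (0.34/6.6 to 0.69/6.6), with the modest error inflation tabulated above. A type I error near 5% needs the more extreme case of a 3:1 ratio with 4 points of drift. The direction cannot be predicted from the protocol.

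**What to change.** Add to sections 12.5.1 and 17.1: *If the allocation ratio between two arms changes while both are open, the models for that comparison will include allocation period and its interaction with visit as fixed effects (or will combine within-period estimates).*

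The interaction is needed because the model uses all visits. A period main effect alone would not remove drift that differs between month 6 and the other visits. The rule should be written before any ratio change, so that it cannot appear data-driven.

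The cost is one or two lines of wording and no extra participants. If the option is used, it takes a few degrees of freedom and about one point of power at 6.6 points for a 2:1 change. If it is not used, it costs nothing.
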